10.1 Safety Parameters

We will assess changes in fibromyalgia symptoms throughout the trial using the Fibromyalgia Impact Questionnaire-Revised (FIQ-R). FIQ-R symptom scores will be logged and reviewed in aggregate by the IMC annually. Significant changes in patient FIQ-R symptom scores will be logged and reported in aggregate to the IMC, IRB, and NCCAM annually. Other safety measures will include verbal contact with the patient throughout the trial. This will be in the form of patients’ response to the questions:

“Since your last acupuncture session, have you experienced a significant worsening change in any of the following?”

- (a) Nausea/Vomiting
- (b) Fainting
- (c) Localized skin infection or bleeding at the site of the treatment
- (d) Increased Pain other than the normal symptoms of fibromyalgia pain

There are no specific laboratory blood tests within this study. As such there will be no safety measures in place to monitor blood outcomes.

Suicidal ideation will be assessed at screening using the Patient Health Questionnaire (PHQ-9). Depression and Anxiety will be assessed at screening, baseline and follow-up. Subjects scoring between 10-14 on the PHQ-9 (“Moderately Depressed”) will be eligible to enroll but will require additional monitoring and will be asked to retake the PHQ-9 at the baseline behavioral visit (visit 1) and the third treatment visit (visit 5), in addition to the scheduled survey administration of visit 0 and visit 11. Subjects scoring between 15-19 (“Moderately Severe” depression) will be referred to the PI for a decision. Should they be enrolled in the study, they will also complete the PHQ-9 at visit 1 and visit 5. Any score above 20 will be considered “Severe” depression, and the subject will not be eligible. Any subject that reports a score of > 0 on question 9 (“Thoughts that you would be better off dead, or of hurting yourself”) of the PHQ-9 will be referred to support services offered by the University of Michigan Hospital System. Any subject deemed ineligible based on their PHQ-9 will be referred to a support services offered by the University of Michigan Hospital System.

10.2 Methods and Timing for Assessing, Recording, and Analyzing Safety Parameters

Acupuncture and electro acupuncture are generally considered safe interventions and as such we do not expect to have many adverse or serious adverse events in our trial. However to assess if participant fibromyalgia pain worsens significantly over the course of the trial, we will administer the FIQ-R once per week during the treatment phase of the study and at each evaluation. This measure will be used for safety purposes only and will not be used as a research data gathering tool. As stated above, if the FIQ-R score displays a clinically significant increase during the course of the trial, we will advise the research participant to seek care from their primary care physician.

The acupuncturist or unblinded team member will complete the post-acupuncture safety assessment at the completion of each treatment administration. This case report form will be reviewed with the unblinded project manager prior to the completion of the treatment visit.

10.3 Adverse Events and Serious Adverse Events

An **adverse event (AE)** is defined as: “Any untoward or unfavorable medical occurrence in a human subject, including any abnormal sign (for example, abnormal physical exam or laboratory finding), symptom, or disease, temporarily associated with the subject’s participation in the research, whether or not considered related to the subject’s participation in the research.” An adverse finding can include a significant change in baseline symptoms, abnormal assessments (such as bruising or minor bleeding with needles), or any combination of these.

Examples of AEs are as follows:

- Changes in the general condition of the patient
- Subjective symptoms offered by or elicited from the patient
- Objective signs observed by the Investigator or other study personnel
- All concurrent diseases that occur after the start of the study, including any change in severity or frequency of preexisting disease such as a clinically significant increase in the FIQ-R score.
- Clinically relevant physical findings that occur during the study, this includes the presentation of known side effects from acupuncture treatment (bleeding, fainting, localized skin infection, increased pain, nausea, or vomiting)

Changes in the pain or occurrence of fibromyalgia symptoms noted in the patient’s baseline self-report questionnaire will be logged as part of the patient’s research record and reported annually. Clinically significant changes, as assessed by the Investigator, will be recorded and assessed for seriousness. This includes the signs and appearance of symptoms of fibromyalgia.

A **serious adverse event (SAE)** is defined as any adverse event that results in one or more of the following outcomes:

- Death
- A life-threatening event
- Inpatient hospitalization or prolongation of existing hospitalization relating to study treatment
- A persistent or significant disability/incapacity hospitalization relating to study treatment
- An important medical event based upon appropriate medical judgment

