10.4 Reporting Procedures

All adverse events, regardless of attribution, will be recorded by the study coordinator in the patients research file using the AE CRF. In addition, AEs will be tracked in aggregate using the AE tracking log.

This log will also document corrective actions required and attribute severity, relatedness and expectedness.

The PI will review and acknowledge (by signing the CRF) all recorded adverse events. The AE Log will be reviewed by the Independent Monitoring Committee annually, or more frequently if requested. The U-M IRB will receive at least an annual summary of all AEs in aggregate. This log will also be included in the annual report to NCCAM.

Serious AEs will be reported within 7-days of the occurrence notification. Unanticipated problems or privacy violations/breach of confidentiality will be treated as serious and also reported within 7-days of occurrence to the appropriate oversight body.

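### Two of the five seriousness criteria require a link to study treatment, so some hospital admissions fall outside 7-day reporting

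*Combined protocol and SAP*

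**What the plan says.** Section 10.3 defines an adverse event (AE) without reference to cause: it counts "whether or not considered related to the subject"'s participation. The SAE definition starts equally broadly; an SAE "is defined as any adverse event that results in one or more of the following outcomes". Five outcomes follow. Death and a life-threatening event have no further condition. Hospitalisation does: "Inpatient hospitalization or prolongation of existing hospitalization relating to study treatment". So does disability: "A persistent or significant disability/incapacity hospitalization relating to study treatment". The last outcome has no causal condition but rests on discretion: "An important medical event based upon appropriate medical judgment".

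Section 10.4 then says "All adverse events, regardless of attribution, will be recorded", and makes relatedness one of the attributes entered in the tracking log, next to severity and expectedness. It ties fast reporting to seriousness: "Serious AEs will be reported within 7-days of the occurrence notification". Unanticipated problems and privacy breaches are handled as serious, also within 7 days. Other AEs reach the monitoring committee through a yearly log review (sooner on request), the IRB through a summary at least once a year, and the funder through the annual report.

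**The concern.** Seriousness describes the outcome of an event; relatedness describes its presumed cause. Section 10.4 keeps them apart, whereas Section 10.3 merges them for two of its five outcomes. Because the 7-day rule depends on seriousness, a judgement of no relation to treatment removes an admission from the hospitalisation criterion, and with it the clearest route to prompt external review.

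What is at stake is the timing of oversight. An independent body is useful partly because it can question an attribution made on site. Under the text as it stands, that attribution can decide whether the body hears of the event within 7 days or at the yearly review. The disability line is also garbled: the word for hospitalisation sits in the middle of it, so a coordinator cannot tell whether disability without admission qualifies.

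**Working it through.** No arithmetic is involved. The check follows the rules in Sections 10.3 to 10.5 for particular kinds of event.

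**Assumption.** Study treatment means electro-acupuncture (EA) or mock laser (ML). The term is not defined, but the Schedule of Evaluations labels the treatment row that way.

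**Step 1: the criteria.** Of the five listed outcomes, three carry no causal condition (death, life-threatening event, important medical event) and two do (hospitalisation, disability/incapacity). The lead-in carries none.

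**Step 2: whose admission cannot meet the hospitalisation criterion.**

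| Admission | Why the criterion is not met | Source |
|---|---|---|
| FM patient on treatment, judged unrelated | The condition fails on attribution | 10.3 |
| Any of the 40 healthy controls | They receive no acupuncture, yet AEs are collected at Visits 1 and 2 | 3.2, 7.1 |
| FM patient before the first treatment | No treatment has been given, yet AEs are collected at Visits 1 and 2 | 3.1, 9.4.2, 9.4.3 |
| Due to MRI or pressure testing | A study procedure is not study treatment, yet MRI-related AEs are collected and a sensory-testing AE is listed as expected | 9.4.3, 9.4.6, 10 |

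The healthy controls are 40 of 40 + 80 = 120 planned participants, one third. The fourth row shows that the condition is also narrower than the AE definition in another way: that definition refers to taking part in the research, whereas the condition refers only to treatment.

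**Step 3: other routes to 7-day reporting.** An admission that fails the criterion is still reported within 7 days if it is fatal, life-threatening, judged an important medical event, or an unanticipated problem. The first two depend on the outcome. The third is expressly a matter of judgement. The fourth could well catch an unexpected procedure-related admission, but an admission judged expected and unrelated may meet none of the four.

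**Step 4: what happens to the remainder.** The event is recorded on the AE form, signed by the PI (10.4) and followed weekly until resolved or stable (10.5). It goes outside the study team through the annual channels unless the committee asks for more. The default interval for outside review is thus up to a year in place of 7 days.

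**The case against.** The strongest reply is that SAEs are a subset of AEs. A narrower test for the subset does not conflict logically with a broad AE definition or with a duty to record everything, and a site can obey both. That is right, and a reader who infers a strict contradiction goes too far. What remains is an inconsistency: the SAE lead-in admits any AE, two bullets beneath it do not, and Section 10.4 already has a separate place for relatedness.

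Second, the gap is limited. Nothing goes unrecorded, the PI sees every event, follow-up is weekly, and three of the five criteria plus the unanticipated-problem rule still apply. This stands, and it confines the point to expedited reporting of a residual group of admissions.

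Third, the condition in the hospitalisation line could be attached only to prolongation of an existing stay. Grammatically this is possible, but its repetition in the disability line favours the restrictive reading. The ambiguity itself needs correcting.

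Fourth, a reader might infer that a relatedness test distorts the EA–ML comparison of serious events, since mock laser involves no skin contact and unblinded staff complete the post-treatment safety form (9.1.3, 10.2). The documents do not support that. Section 11 plans no comparison of SAEs. No section assigns the relatedness decision for an admission to unblinded staff, and the PIs who sign the events are blinded until database lock (9.1.1, 10.4). Since all AEs are recorded, admissions by arm can still be counted.

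Finally, Section 10.6 (Safety Monitoring) and the Data Safety Monitoring Plan (Appendix A) were not available to this review. Either may define SAEs without the condition. If so, Section 10.3 still needs to be brought into line with it.

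**Conclusion.** The point holds as an internal inconsistency with a practical effect on reporting. Two of the five seriousness criteria depend on attribution to treatment. Admissions judged unrelated to EA or ML, including all those in healthy controls, before the first treatment or due to a study procedure, fail the hospitalisation criterion. Those that no other route catches move from 7-day reporting to annual channels.

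The number of such events cannot be estimated, because the documents give no rate; Section 10.2 expects few adverse or serious events. The conclusion rests on the natural reading of the two lines, on study treatment meaning EA or ML, and on the text available. It does not extend to events being lost from the record, nor to any bias in a planned analysis; no endpoint or power statement is touched. It is worth correcting because it concerns a stated safety rule and the correction is easy.

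**What to change.** Reconcile Section 10.3 with Section 10.4:

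- Remove the relatedness condition from the hospitalisation and disability/incapacity criteria, so that seriousness depends on outcome alone.
- Rewrite the disability line so that it states one criterion, without the stray reference to hospitalisation.
- Keep relatedness where Section 10.4 already puts it, as a separate entry in the AE log.
- Check that the revised wording agrees with Section 10.6 and the Data Safety Monitoring Plan, and align whichever differs.

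The cost is a wording amendment and possibly a few more expedited reports. No change to visits, data collection or analysis is needed.

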10.4 Reporting Procedures

All adverse events, regardless of attribution, will be recorded by the study coordinator in the patients research file using the AE CRF. In addition, AEs will be tracked in aggregate using the AE tracking log.

This log will also document corrective actions required and attribute severity, relatedness and expectedness.

The PI will review and acknowledge (by signing the CRF) all recorded adverse events. The AE Log will be reviewed by the Independent Monitoring Committee annually, or more frequently if requested. The U-M IRB will receive at least an annual summary of all AEs in aggregate. This log will also be included in the annual report to NCCAM.

Serious AEs will be reported within 7-days of the occurrence notification. Unanticipated problems or privacy violations/breach of confidentiality will be treated as serious and also reported within 7-days of occurrence to the appropriate oversight body.

10.5 Follow Up for Adverse Events

Any participant that has an adverse event will be followed weekly until either the event has resolved or the event is considered stable by the participant and the research team. Adverse events that persist for an extended duration (such as over the duration of the study) will also be followed weekly until either the event is resolved or considered stable by the PI and the research participant.

11. STATISTICAL CONSIDERATIONS

11.1. Aim 1: At baseline, characterize altered somatosensory neurocircuitry underlying chronic pain in FM.

Hypothesis 1: Using resting fcMRI, the insula in FM patients will show more correlation with DMN, and more anti-correlation with SMN, compared to HC.

We will use dual-regression independent component analysis (ICA) to evaluate resting connectivity between DMN/SMN and insula. Two-sample t-tests will compare FM vs. HC, cluster-corrected at $p=0.05$.

Based on our previous studies, assuming DMN connectivity z score (middle insula region) of 1 for a fibromyalgia patient vs. 0.5 for a healthy control with a common standard deviation of 0.5, we will expect a typical relative effect of 1 (mean ICA-derived z score over its standard deviation). Similar effects (negative connectivity values) are expected for SMN-derived biomarkers. With the planned numbers of subjects we will have the power exceeding 97% to detect the effects by a two-sided t-test.

Hypothesis 2: Using $^1\text{H-MRS}$, FM patients will show pain related increased Glx and reduced levels of GABA within the insula and S2 as compared to HC.

Metabolite concentration from regions of interest will be assessed using spectra data input into LCModel. A two-sample T-test will compare FM vs. HC, significant at $p=0.05$.

Our sample size calculation for difference between FM and HC assumes (from pilot data) that Glx, a proxy for glutamate concentration, has mean(SD) = 10.5(1.4) in arbitrary institutional units (AIU) and a FM-HC relative difference in excess of 10%. Thus we conservatively hypothesize an average Glx around 11.5 AIU and GABA around 1.3 mmol/kg in the FM group. We conclude that we will have the power of at least 84% for the GABA and 81% for the Glx based on a two-sided t-test with unequal N (80 in FM vs. 20 in HC) at the significance level of 0.05.

Hypothesis 3: Using evoked pain fMRI, FM patients will be more sensitive to evoked pressure pain and demonstrate greater insula activation to pain stimuli, compared to HC.

A general linear model will assess brain response to experimental pain from a block design BOLD fMRI run. A group level FM - HC difference map will use a two sample t-test, cluster corrected at $p=0.05$.

Changes in connectivity z-score for a typical connectivity biomarker are expected to follow a different slope in FM vs. HC patients in response to pressure pain. Based on our previous studies we expect the slope of 1.3 vs. 0.8 (FM vs. HC, respectively) with the standard deviation of the pain score of approximately 1 and standard deviation of the connectivity score at a given level of pressure pain of around 0.5. This ensures we will have over 86% power to detect a difference in connectivity responses to evoked pain.

ROC Analysis

In order to characterize the potential of biomarkers to predict the disease, a decision rule predicting FM status, a binary outcome, based on connectivity, Glx/GABA and evoked pain biomarkers. Our primary method for rule development will be logistic regression. Stepwise variable selection procedures using Likelihood Ratio tests and Akaike Information Criterion (AIC) will be performed to identify the set of significant predictors. A cutpoint on the linear predictor in the logistic model will define the decision rule with values above the cutpoint for a particular subject interpreted as prediction of treatment success for the subject. A set of rules obtained by varying the cutpoint will be summarized by the Receiver-Operating-Characteristic (ROC) curve plotting sensitivity by 1-specificity of the rule. The area under the ROC for the model will characterize the quality of prediction. The area under the ROC will serve as the overall measure of discriminative ability of the model. In order to obtain a realistic estimate of ROC, cross-validation will be used when estimating sensitivity and specificity corresponding to various cutoff values.

The assessment of power is based on a test for area under the ROC. We hypothesize that an area of 0.7 can be achieved. A test for area <0.6 vs. >0.6 shows that we will have 83% power to discriminate area of 0.7 from 0.6 or less with 80 FM patients and 20 controls, using a two-sided test at the significance level of 0.05. This indicates that we will have the precision of at least 0.1 on the area under ROC scale.

11.2. Aim 2: Evaluate longitudinal desensitization effects of electro- and mock laser acupuncture interventions on the neurocircuitry underlying chronic pain in FM, correlate the change in pain with changes in neurocircuitry physiology, study neuroimaging biomarkers as mediators for the treatment effect.

This aim evaluates a *mechanistic* value of the neuroimaging biomarkers by studying their response to treatment and correlation between the change in biomarker measurements and changes in pain induced by treatments, and biomarker mediation effects.

Hypothesis 1: EA, which involves greater somatosensory afference, will more readily reduce resting insula connectivity to SMN and DMN compared to ML. The change in pain will correlate with change in insula connectivity for EA, but not ML. Insula connectivity will represent a mediator for the treatment effect.

Treatment effects on connectivity

We will perform dual-regression ICA with group level estimates for baseline and post-treatment fcMRI data (DMN and SMN) entered into a linear mixed model with factors STIM (levels EA, ML) and TIME (levels baseline and post-therapy). Time by treatment interaction effect will be of main interest in the analysis. If a significant main effect or interaction is found, we will perform post-hoc difference map analyses, to evaluate which group produced the greatest change in resting connectivity.

Power analysis for fcMRI is based on data from the preliminary study on intrinsic connectivity and its short-term response to acupuncture. From preliminary data on 15 subjects, we estimate the SD of the number of voxels activated before and after acupuncture in the default mode independent component to be 2860 and 4559, respectively. The covariance between these before and after counts is 3388878. This implies the standard deviation of the within-subject change in connectivity of $\sqrt{2860^2+4559^2-2*3388878}=4710$. Based on the same data, we find the before and after means to be 7078 and 9844, respectively. Then, a two-sided paired t-test for the presence of change will have the effect size of 0.6 and the power of 95% with 40 patients in the EA group.

Based the similar mean connectivity difference of around 3000 between ML and EA, and the same SD of 4710 we will have 80% power to detect the difference between treatments with respect to the mean within-patient change in connectivity.

Correlation with pain

A linear mixed model will be used to regress BPI pain measurements on the neuro-imaging biomarkers. Correlation between clinical pain and biomarkers is the primary target.

We hypothesize a correlation coefficient of at least 0.5 between pain and connectivity z score in the EA arm. This will give us 94% power to detect the correlation.

Interim analysis. After 50% of the subjects have been enrolled and evaluated, we will determine if fcMRI outcome metrics are sensitive enough to continue using for the biomarker for the duration of the study. Screening of biomarkers (brain regions) will be done by computing a post-hoc power based on 20 patients per arm. Biomarkers showing post-hoc power lower than 20% will not be pursued further. This decision corresponds to dropping biomarkers showing correlation coefficients less than 0.18 in the interim analysis.

Mediation Analysis

In the linear mixed model regressing BPI pain score on treatment and time, the effect of treatment on pain is expressed as a regression coefficient for time specific to treatment group (or a treatment by time interaction). Mediation effect will be measured as the proportion of treatment effect explained by the biomarker (PTE) representing a relative change in the regression coefficient when biomarker is included in the model (relative to the coefficient before biomarker inclusion into the model). Standard error for the PTE will be estimated by bootstrap, and a two-sided 95% interval for the effect will be constructed. Wald test with the statistic of the form (change in regression coefficient)/(bootstrap SE) will be used to test for the mediation effect. Similar analyses will be done using a logistic regression model with clinically relevant reduction in pain (defined as 50% and 30%) as a response.

Power. We use Sobel's test based on linear regression to compute power. Power analysis targets biomarkers with the mediation effect of PTE=0.5. We assume that the regression coefficient in the model for the treatment effect on connectivity is 3000; treatment effect beta in the model of change in pain excluding the biomarker is 2; standard deviation of the randomized treatment variable 0.5; standard deviation of the change in connectivity over time 4500 voxels; squared the correlation between the treatment variable and the change in connectivity $3.7e-05$; standard deviation of errors in the full model regressing change in pain on both treatment and the biomarker 1.5. These assumptions are consistent with the ones made previously in the power calculations related to different lags of the mediation analysis, with our preliminary data, and with the acupuncture effects on pain reported in the literature. Under these assumptions we will have the power of 81% to detect the mediation effect by Sobel's test.[114]

Hypothesis 2 : EA will more readily reduce Glx and increase GABA in the insula as compared to ML, which will not reduce Glx and GABA. The change in pain will correlate with change in insula GABA and Glx for EA but not ML. Glx and GABA will represent mediators for the treatment effect on change in pain.

Similar to above, linear mixed models and paired t-test analyses will evaluate, separately, Glx and GABA concentration levels taken from baseline and post-therapy H-¹MRS scans.

A reduction in the Glx of about 1.5 arbitrary institutional units (AIU) with a standard deviation not exceeding 0.6 is expected in the EA group. At the same time in the ML group a much smaller effect is expected (around 1 AIU, same standard deviation). This ensures 95% power when using a two –sided test. A similar analysis for differences in the change in GABA of 0.3 vs. 0.1 mmol/kg with a standard deviation of 0.25 gives 94% power to detect a difference.

Correlation between Glx/GABA and clinical pain (BPI) will be analyzed similar to the fcMRI biomarkers. The study has 94% power to detect correlations of 0.5 and higher.

Similar to fcMRI biomarkers, if Glx or GABA show less than 20% post-hoc power after half of the patients have been measured (correlation less than 0.18), their longitudinal measurements will be discontinued for the remaining patients.

Mediation Analysis is similar to the one proposed for connectivity.

Hypothesis 3: EA will more readily reduce pain-evoked fMRI activation in the insula as compared to ML, which will not reduce pain-evoked fMRI activation. The change in pain will correlate with change in insula response to evoked pain for EA but not ML. Insula response to evoked pain will represent a mediator for the treatment effect on change in pain.

Parameter estimates from evoked pain block-design fMRI scans will be used in a linear mixed model and post-hoc paired t-tests, similar to the approach described above.

Changes in connectivity z-score for a typical connectivity biomarker are expected to follow a different slope in EA vs. ML patients in response to pressure pain. Assuming the slope of 1.3 vs. 0.5 with the standard deviation of the pain score of approximately 1 and standard deviation of the connectivity z score at a given level of pressure pain of around 1. This ensures we will have over 94% power to detect a difference in connectivity by pressure pain slope responses with 40 patients per treatment group.

Change in pain-evoked fMRI activation will be correlated with the change in clinical pain. To do this evoked pain responses will be added as covariates into the linear mixed model regressing BPI pain on other covariates.

Mediation Analysis is similar to the one proposed for connectivity.

11.3. Aim 3: Evaluate the ability of altered neurocircuitry at baseline to predict clinical response.

This aim evaluates a *predictive* value of the neuroimaging biomarkers by studying whether their measurements at baseline correlate with pain responses to treatments.

Hypothesis 1: Greater baseline DMN-insula/S2 connectivity and SMN-insula/S2 anti-correlation, will display greater clinical response to EA vs. ML

We will use baseline estimates of DMN and SMN connectivity, taken from the dual regression ICA analysis, as independent variable in a multiple regression model with dependent variable set as the change score (post-therapy – baseline) for clinical pain (Brief Pain Inventory; BPI). Regression slopes will be contrast between different pairs (e.g. EA vs. ML) set in the same regression model. We will explore within-group correlations for individual therapies if the difference map for any two therapies is significant, at cluster corrected $p=0.05$.

Hypothesis 2: FM patients with greater baseline insular and S2 Glx/GABA ratios will display greater clinical response to EA as compared to ML.

An identical approach will be used as for hypothesis 1 above, but with Glx/GABA ratio as dependent variable.

Hypothesis 3: FM patients with greater baseline pain-evoked insular activation will display greater clinical response to EA as compared to ML.

An ROI analysis will determine baseline insula response to evoked pain. This parameter estimate will then be used as a dependent variable in an identical multiple linear regression approach, as detailed above.

Power. The expectations for correlations between the baseline measurements of biomarkers and clinical pain responses are set similar to the mechanistic setting. We expect to uncover correlations of 0.5 between measurements at baseline and the change in pain in response to treatment (mainly in the EA arm). We will have 94% power to detect such correlations.

Interim analysis. Similar to the mechanistic study we will conduct an interim analysis after 20 patients in each arm have been measured. Given the focus of this study on mechanistic value of the biomarkers, mechanistic analysis will take priority to the predictive setting, and the results of the predictive interim analysis will be treated informally. A study team decision will be issued on biomarkers that do show mechanistic value yet do not make the cut in the predictive analysis.

